Ocular event, Grade 1	
 • Continue atezolizumab. • Patient referral to ophthalmologist is strongly recommended. • Initiate treatment with topical corticosteroid eye drops and topical immunosuppressive therapy. • If symptoms persist, treat as a Grade 2 event.
Ocular event, Grade 2	
 • Withhold atezolizumab for up to 12 weeks after event onset.^a • Patient referral to ophthalmologist is strongly recommended. • Initiate treatment with topical corticosteroid eye drops and topical immunosuppressive therapy. • If event resolves to Grade 1 or better, resume atezolizumab.^b • If event does not resolve to Grade 1 or better while withholding atezolizumab, permanently discontinue atezolizumab and contact Medical Monitor.^c
Ocular event, Grade 3 or 4	
 • Permanently discontinue atezolizumab and contact Medical Monitor.^c • Refer patient to ophthalmologist. • Initiate treatment with 1–2 mg/kg/day oral prednisone or equivalent. • If event resolves to Grade 1 or better, taper corticosteroids over ≥ 1 month.

^a Atezolizumab may be withheld for a longer period of time (i.e., > 12 weeks after event onset) to allow for corticosteroids (if initiated) to be reduced to ≤ 10 mg/day oral prednisone or equivalent. The acceptable length of the extended period of time must be agreed upon by the investigator and the Medical Monitor.

^b If corticosteroids have been initiated, they must be tapered over ≥ 1 month to ≤ 10 mg/day oral prednisone or equivalent before atezolizumab can be resumed.

^c Resumption of atezolizumab may be considered in patients who are deriving benefit and have fully recovered from the immune-related event. Patients can be re-challenged with atezolizumab only after approval has been documented by both the investigator (or an appropriate delegate) and the Medical Monitor.

APPENDIX 8

Management of Atezolizumab-Specific Adverse Events (cont.)

IMMUNE-RELATED MYOCARDITIS

Immune-related myocarditis has been associated with the administration of atezolizumab. Immune-related myocarditis should be suspected in any patient presenting with signs or symptoms suggestive of myocarditis, including, but not limited to, dyspnea, chest pain, palpitations, fatigue, decreased exercise tolerance, or syncope. Immune-related myocarditis needs to be distinguished from myocarditis resulting from infection (commonly viral, e.g., in a patient who reports a recent history of GI illness), ischemic events, underlying arrhythmias, exacerbation of preexisting cardiac conditions, or progression of malignancy.

All patients with possible myocarditis should be urgently evaluated by performing cardiac enzyme assessment, an ECG, a chest X-ray, an echocardiogram, and a cardiac MRI as appropriate per institutional guidelines. A cardiologist should be consulted. An endomyocardial biopsy may be considered to enable a definitive diagnosis and appropriate treatment, if clinically indicated.

Patients with signs and symptoms of myocarditis, in the absence of an identified alternate etiology, should be treated according to the guidelines in [Table 6](#).

APPENDIX 8
Management of Atezolizumab-Specific Adverse Events (cont.)

Table 6 Management Guidelines for Immune-Related Myocarditis

Event	Management
Immune-related myocarditis, Grade 1	
 • Refer patient to cardiologist. • Initiate treatment as per institutional guidelines.
Immune-related myocarditis, Grade 2	
 • Withhold atezolizumab for up to 12 weeks after event onset^a and contact Medical Monitor. • Refer patient to cardiologist. • Initiate treatment as per institutional guidelines and consider antiarrhythmic drugs, temporary pacemaker, ECMO, or VAD as appropriate. • Consider treatment with 1–2 mg/kg/day IV methylprednisolone or equivalent and convert to 1–2 mg/kg/day oral prednisone or equivalent upon improvement.^a • If event resolves to Grade 1 or better, resume atezolizumab.^b • If event does not resolve to Grade 1 or better while withholding atezolizumab, permanently discontinue atezolizumab and contact Medical Monitor.^c
Immune-related myocarditis, Grade 3-4	
 • Permanently discontinue atezolizumab and contact Medical Monitor.^c • Refer patient to cardiologist. • Initiate treatment as per institutional guidelines and consider antiarrhythmic drugs, temporary pacemaker, ECMO, or VAD as appropriate. • Initiate treatment with 1–2 mg/kg/day IV methylprednisolone or equivalent and convert to 1–2 mg/kg/day oral prednisone or equivalent upon improvement.^{a,b} • If event does not improve within 48 hours after initiating corticosteroids, consider adding an immunosuppressive agent. • If event resolves to Grade 1 or better, taper corticosteroids over ≥ 1 month.

ECMO=extracorporeal membrane oxygenation; VAD=ventricular assist device.

^a Atezolizumab may be withheld for a longer period of time (i.e., > 12 weeks after event onset) to allow for corticosteroids (if initiated) to be reduced to ≤ 10 mg/day oral prednisone or equivalent. The acceptable length of the extended period of time must be agreed upon by the investigator and the Medical Monitor.

^b If corticosteroids have been initiated, they must be tapered over ≥ 1 month to ≤ 10 mg/day oral prednisone or equivalent before atezolizumab can be resumed.

^c Resumption of atezolizumab may be considered in patients who are deriving benefit and have fully recovered from the immune-related event. Patients can be re-challenged with atezolizumab only after approval has been documented by both the investigator (or an appropriate delegate) and the Medical Monitor.

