4.1.1 Inclusion Criteria

Patients must meet all of the following criteria to be eligible for study entry:

- Signed Informed Consent Form
- Age \geq 18 years
- ECOG performance status of 0 or 1
- Histologically or cytologically confirmed Stage IIIB–IVB NSCLC (based on the IASLC Lung Cancer Staging Project proposed for the eighth edition of the AJCC NSCLC staging see [Appendix 3](#))
 - Patients with histologically or cytologically confirmed Stage IIIB-IV NSCLC based on the seventh edition of the AJCC NSCLC staging system are also eligible for study entry.
- For patients who have received prior neo-adjuvant/adjuvant chemotherapy or chemoradiotherapy with curative intent for non-metastatic disease: a treatment-free interval of at least 6 months prior to enrollment.
- Patients with any PD-L1 test result by IHC are eligible for the study.
- Patients without a PD-L1 test result are eligible for the study.
- Measurable disease, as defined by RECIST v1.1 (based on the assessments detailed in Section [4.5.5](#)).
 - Previously irradiated lesions can only be considered measurable disease if disease progression has been unequivocally documented at that site since radiation and the previously irradiated lesion is not the only site of measurable disease
- Adequate hematologic and end-organ function, defined by the following laboratory test results obtained within 14 days prior to the first dose of study drug:
 - ANC \geq 1500 cells/ μ L without granulocyte colony-stimulating factor support
 - Lymphocyte count \geq 500 cells/ μ L
 - Platelet count \geq 100,000 cells/ μ L without transfusion
 - Hemoglobin \geq 9.0 g/dL

Patients may be transfused to meet this criterion.

- International normalized ratio (INR) or activated partial thromboplastin time (aPTT) $\leq 1.5 \times$ the upper limit of normal (ULN)

This applies only to patients who are not receiving therapeutic anticoagulation; patients receiving therapeutic anticoagulation must have an INR or aPTT within therapeutic limits for at least 1 week prior to enrollment.
- AST, ALT, and alkaline phosphatase $\leq 2.5 \times$ ULN with the following exceptions:

Patients with documented liver metastases: AST and/or ALT $\leq 5 \times$ ULN

Patients with documented liver or bone metastases: alkaline phosphatase $\leq 5 \times$ ULN
- Serum bilirubin $\leq 1.5 \times$ ULN

Patients with known Gilbert disease who have a serum bilirubin level $\leq 3 \times$ ULN may be enrolled.
- Calculated creatinine clearance ≥ 30 mL/min

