5.2.3 Adverse Events of Special Interest (Immediately Reportable to the Sponsor)

Adverse events of special interest are required to be reported by the investigator to the Sponsor immediately (i.e., no more than 24 hours after learning of the event; see Section 5.3.5.4 for reporting instructions). Adverse events of special interest for this study include the following:

- Any of the following confirmed treatment-emergent autoimmune conditions:
 - Pneumonitis
 - Colitis
 - Endocrinopathies: diabetes mellitus, pancreatitis, or adrenal insufficiency or hyperthyroidism
 - Hepatitis
 - Transaminitis: Grade ≥ 2 (AST or ALT $>3 \times$ ULN and bilirubin $>2 \times$ ULN) OR AST or ALT $>10 \times$ ULN
 - Systemic lupus erythematosus
 - Neurologic: Guillain-Barré syndrome, myasthenia gravis, meningoencephalitis
 - Nephritis
- Events suggestive of hypersensitivity, cytokine release, influenza-like illness, systemic inflammatory response system, systemic immune activation, or infusion-reaction syndromes

- Cases of potential drug-induced liver injury that include an elevated ALT or AST in combination with either an elevated bilirubin or clinical jaundice, as defined by Hy's law (see Section 5.3.5.7)
- Suspected transmission of an infectious agent by the study drug, as defined below:
 - Any organism, virus, or infectious particle (e.g., prion protein transmitting transmissible spongiform encephalopathy), pathogenic or non-pathogenic, is considered an infectious agent. A transmission of an infectious agent may be suspected from clinical symptoms or laboratory findings that indicate an infection in a patient exposed to a medicinal product. This term applies only when a contamination of the study drug is suspected.

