5.3.3 Assessment of Severity of Adverse Events

The adverse event severity grading scale for NCI CTCAE v4.0 will be used for assessing adverse event severity. [Table 5](#) will be used for assessing severity for adverse events that are not specifically listed in the NCI CTCAE.

Table 5 Adverse Event Severity Grading Scale for Events Not Specifically Listed in the NCI CTCAE

Grade	Severity
1	Mild; asymptomatic or mild symptoms; clinical or diagnostic observations only; or intervention not indicated
2	Moderate; minimal, local, or non-invasive intervention indicated; or limiting age-appropriate instrumental activities of daily living ^a
3	Severe or medically significant, but not immediately life-threatening; hospitalization or prolongation of hospitalization indicated; disabling; or limiting self-care activities of daily living ^{b,c}
4	Life-threatening consequences or urgent intervention indicated ^d
5	Death related to adverse event ^d

NCI CTCAE = National Cancer Institute Common Terminology Criteria for Adverse Events.
 Note: Based on the most recent version of the NCI CTCAE (v 4.0), which can be found at: http://ctep.cancer.gov/protocolDevelopment/electronic_applications/ctc.htm

- ^a Instrumental activities of daily living refers to preparing meals, shopping for groceries or clothes, using the telephone, managing money, etc.
- ^b Examples of self-care activities of daily living include bathing, dressing and undressing, feeding oneself, using the toilet, and taking medications, as performed by patients who are not bedridden.
- ^c If an event is assessed as a "significant medical event," it must be reported as a serious adverse event (see Section 5.4.2 for reporting instructions), per the definition of serious adverse event in Section 5.2.2.
- ^d Grade 5 events must be reported as serious adverse events (see Section 5.4.2 for reporting instructions), per the definition of serious adverse event in Section 5.2.2.

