APPENDIX 8 Management of Atezolizumab-Specific Adverse Events (cont.)

HEPATIC EVENTS

Immune-related hepatitis has been associated with the administration of atezolizumab. Eligible patients must have adequate liver function, as manifested by measurements of total bilirubin and hepatic transaminases, and liver function will be monitored throughout study treatment. Management guidelines for hepatic events are provided in [Table 2](#).

Patients with right upper-quadrant abdominal pain and/or unexplained nausea or vomiting should have liver function tests (LFTs) performed immediately and reviewed before administration of the next dose of study drug.

For patients with elevated LFTs, concurrent medication, viral hepatitis, and toxic or neoplastic etiologies should be considered and addressed, as appropriate.

Table 2 Management Guidelines for Hepatic Events

Event	Management
Hepatic event, Grade 1	
 • Continue atezolizumab. • Monitor LFTs until values resolve to within normal limits.
Hepatic event, Grade 2	
All events:
 
 • Monitor LFTs more frequently until return to baseline values. 
Events of > 5 days' duration:
 
 • Withhold atezolizumab for up to 12 weeks after event onset. ^a • Initiate treatment with 1–2 mg/kg/day oral prednisone or equivalent. • If event resolves to Grade 1 or better, resume atezolizumab. ^b • If event does not resolve to Grade 1 or better while withholding atezolizumab, permanently discontinue atezolizumab and contact Medical Monitor. ^c

LFT=liver function tests.

^a Atezolizumab may be withheld for a longer period of time (i.e., > 12 weeks after event onset) to allow for corticosteroids (if initiated) to be reduced to ≤ 10 mg/day oral prednisone or equivalent. The acceptable length of the extended period of time must be agreed upon by the investigator and the Medical Monitor.

^b If corticosteroids have been initiated, they must be tapered over ≥ 1 month to ≤ 10 mg/day oral prednisone or equivalent before atezolizumab can be resumed.

^c Resumption of atezolizumab may be considered in patients who are deriving benefit and have fully recovered from the immune-related event. Patients can be re-challenged with atezolizumab only after approval has been documented by both the investigator (or an appropriate delegate) and the Medical Monitor.

APPENDIX 8
Management of Atezolizumab-Specific Adverse Events (cont.)

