Table 2 Management Guidelines for Hepatic Events (cont.)

Event	Management
Hepatic event, Grade 3 or 4	
 • Permanently discontinue atezolizumab and contact Medical Monitor. ^c • Consider patient referral to gastrointestinal specialist for evaluation and liver biopsy to establish etiology of hepatic injury. • Initiate treatment with 1–2 mg/kg/day oral prednisone or equivalent. • If event does not improve within 48 hours after initiating corticosteroids, consider adding an immunosuppressive agent. • If event resolves to Grade 1 or better, taper corticosteroids over ≥ 1 month.

LFT=liver function tests.

- ^a Atezolizumab may be withheld for a longer period of time (i.e., > 12 weeks after event onset) to allow for corticosteroids (if initiated) to be reduced to ≤ 10 mg/day oral prednisone or equivalent. The acceptable length of the extended period of time must be agreed upon by the investigator and the Medical Monitor.
- ^b If corticosteroids have been initiated, they must be tapered over ≥ 1 month to ≤ 10 mg/day oral prednisone or equivalent before atezolizumab can be resumed.
- ^c Resumption of atezolizumab may be considered in patients who are deriving benefit and have fully recovered from the immune-related event. Patients can be re-challenged with atezolizumab only after approval has been documented by both the investigator (or an appropriate delegate) and the Medical Monitor.

GASTROINTESTINAL EVENTS

Immune-related colitis has been associated with the administration of atezolizumab. Management guidelines for diarrhea or colitis are provided in [Table 3](#).

All events of diarrhea or colitis should be thoroughly evaluated for other more common etiologies. For events of significant duration or magnitude or associated with signs of systemic inflammation or acute-phase reactants (e.g., increased C-reactive protein, platelet count, or bandemia): Perform sigmoidoscopy (or colonoscopy, if appropriate) with colonic biopsy, with three to five specimens for standard paraffin block to check for inflammation and lymphocytic infiltrates to confirm colitis diagnosis.

APPENDIX 8
Management of Atezolizumab-Specific Adverse Events (cont.)

Table 3 Management Guidelines for Gastrointestinal Events (Diarrhea or Colitis)

Event	Management
Diarrhea or colitis, Grade 1	
 • Continue atezolizumab. • Initiate symptomatic treatment. • Endoscopy is recommended if symptoms persist for >7 days. • Monitor closely.

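### Patients with liver metastases may enter with AST/ALT up to 5 × ULN, but Appendix 8 Table 2 restarts drug by grade alone, so some would have to recover to below their entry level

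*Protocol*

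**What the plan says.** **Entry.** Protocol Section 4.1.1 caps AST and ALT at 2.5 × ULN but makes an exception, "Patients with documented liver metastases: AST and/or ALT" up to 5 × ULN.

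**Grading.** Section 5.3.3 states: "The adverse event severity grading scale for NCI CTCAE v4.0 will be used for assessing adverse event severity". No adjustment for a raised baseline is given.

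**Action on treatment (Appendix 8, Table 2).**
- Grade 1: continue, and monitor liver tests until they are normal.
- Grade 2, all events: "Monitor LFTs more frequently until return to baseline values".
- Grade 2 for more than 5 days: withhold, start oral corticosteroids, and resume once the event is Grade 1 or better. Failing that, "If event does not resolve to Grade 1 or better while withholding atezolizumab, permanently discontinue atezolizumab and contact Medical Monitor".
- Grade 3 or 4: "Permanently discontinue atezolizumab and contact Medical Monitor".

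Footnote c to the permanent-stop instructions lets resumption be considered for a patient who is benefiting and has recovered fully, with documented approval by the investigator and the Medical Monitor. Full recovery is not defined against baseline.

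**Other sections.** Section 5.3.5.5 requires a change from baseline before a laboratory value must be reported as an adverse event. Section 5.3.5.7 sets the transaminase part of its liver-injury criterion at more than 3 × the baseline value. Section 5.5.1 counts an adverse event as resolved at the baseline grade or better.

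**The concern.** The entry rule deliberately admits a group whose transaminases may already exceed what the on-treatment rule accepts for restarting. After a qualifying Grade 2 event, such a patient can return exactly to the admission value and still not meet the resume condition. As written, the table then leads to permanent discontinuation.

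The reference level also changes from place to place: normal limits in the Grade 1 row, baseline for monitoring in the Grade 2 row, grade for restarting in that same row, and baseline in Sections 5.3.5.5, 5.3.5.7 and 5.5.1. Two sites could read the text reasonably and treat the same patient differently.

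At stake are loss of study drug and exposure to systemic corticosteroids, which Section 4.4.2 says may attenuate the benefit of atezolizumab. Exposure and safety data in this subgroup would also be handled inconsistently.

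**Working it through.** The plan gives no figure to reproduce. The check compares the entry ceiling with the recovery level.

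**Inputs**
- Entry ceiling for AST/ALT: 5 × ULN with documented liver metastases, 2.5 × ULN otherwise (Section 4.1.1).
- Condition for resuming after a Grade 2 event of more than 5 days: Grade 1 or better (Appendix 8, Table 2).
- Grade 1 ceiling C: assumed to be 3 × ULN. The CTCAE transaminase cut-points are not printed in the protocol. The only boundary shown is in Section 5.2.3, under "Transaminitis: Grade" 2 or higher, which names AST or ALT above 3 × ULN. That line defines an event of special interest and also requires bilirubin above 2 × ULN, so it is not a general grading rule.

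**Step 1: required fall below entry.** For an entry value E above C, the smallest fall that meets the resume condition is 1 − C/E.

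| Entry E (× ULN) | C/E with C = 3 | Fall below entry needed to resume |
|---|---|---|
| 3.5 | 3/3.5 = 0.857 | at least 14% |
| 4 | 3/4 = 0.75 | at least 25% |
| 5 | 3/5 = 0.60 | at least 40% |

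A full return to baseline is a fall of 0% below entry, so it fails in every row.

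**Step 2: dependence on the assumed ceiling.**

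| Grade 1 ceiling C (× ULN) | Entry values affected (× ULN) |
|---|---|
| 2.5 | above 2.5, up to 5 |
| 3 | above 3, up to 5 |
| 4 | above 4, up to 5 |

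The window is non-empty for any C below 5. Over these ceilings, patients without liver metastases (entry at most 2.5 × ULN) are not affected.

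**Step 3: spread between references.** For entry at 4 × ULN, the transaminase part of the Section 5.3.5.7 criterion is passed only above 3 × 4 = 12 × ULN. The monitoring target in the Grade 2 row is 4 × ULN. The resume level in that row is 3 × ULN under the assumption. These rules serve different purposes, but nothing says how they fit together for this patient.

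**Step 4: number of patients.** The documents do not give it. Assume 10–25% of 150 patients have liver metastases and 5–15% of those enter above 3 × ULN:
- low: 150 × 0.10 × 0.05 = 0.75
- high: 150 × 0.25 × 0.15 = 5.6

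That is about 1 to 6 patients in the entry window. Only those who then have a qualifying hepatic event meet the rule.

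**The case against.** **The rules are not triggered by the entry value itself.** This stands. Under Section 5.3.5.5 a laboratory value must change from baseline, and under Section 5.3.5.9 a preexisting condition must worsen. A reader might infer that a stable admission value of 4 × ULN already calls for withholding; the documents do not support that. Appendix 8 also asks that neoplastic causes of raised liver tests be considered. That adds work-up but changes no action row.

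**Permanent is not quite permanent.** This stands in part. Footnote c allows re-challenge, and footnote a allows a longer hold while corticosteroids are reduced. But re-challenge is discretionary, needs two approvals and depends on an undefined full recovery. Neither footnote changes the resume condition.

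**Monitoring and redosing may have different endpoints, and a stricter level for redosing may be deliberate.** This is a fair point: different targets for different actions are not in themselves contradictory. But nothing shows that the choice was made with the 5 × ULN exception in mind.

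**A small rise could reach the Grade 3 row.** A reader might infer this for patients entering near 5 × ULN. The documents do not print the Grade 3 cut-point, so it cannot be shown from them and is not part of the point.

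**ORR and PFS would be depressed.** A reader might infer this too, but the size does not support it. Take 6 patients, an assumed ORR of 20%, and every response lost: 6 × 0.20 = 1.2 responders, and 1.2/150 = 0.8 percentage points. The planned confidence-interval half-width is up to 8 points. Patients who stop for toxicity also continue scheduled tumor assessments (Section 3.1).

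**Conclusion.** The mismatch is real but narrow. It concerns patients with documented liver metastases who enter above the Grade 1 ceiling, worsen from baseline, and have a Grade 2 hepatic event lasting more than 5 days. For them, return to baseline does not satisfy the restart rule, and the table then directs permanent discontinuation, subject only to discretionary re-challenge.

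The 14%, 25% and 40% figures rest on the assumed 3 × ULN ceiling. The mismatch itself needs only a ceiling below 5 × ULN. The number affected is unknown and probably a few at most, and no material effect on the efficacy endpoints is claimed. The point should be corrected because the rule, followed as written, disadvantages patients whom the protocol chose to admit, and because sites cannot tell which reference applies.

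**What to change.** Reconcile Section 4.1.1 and Appendix 8 Table 2 with each other and with Sections 5.3.5.5, 5.3.5.7 and 5.5.1. For patients admitted with raised transaminases, the sponsor's medical team should state which reference, absolute grade or the patient's own baseline, governs each hepatic row: the Grade 1 and Grade 2 monitoring targets, the hold, the resume condition and the stop. It should also say what full recovery means in footnote c for these patients. Which reference or threshold is right is a clinical decision, and none is proposed here.

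The cost is amendment wording, mainly in one table, with no new procedures, visits or data.
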